### **9.6.2 Determining the health effect**

The health effect is defined as the projected reduction in HIV incidence over time associated with adopting the intervention relative to standard of care. This will be estimated in our dynamic modeling activities and quantified by two key model outcomes: the number of infections averted per unit person-time on the intervention and the number needed to treat on PrEP@Home to prevent one new infection. The base, standard of care, model will estimate the number of infections expected in the absence of the intervention, and may vary under different assumptions of baseline, clinic-based PrEP coverage outside of the intervention. Each sensitivity analysis in the epidemic model (varying levels of access, coverage, and adherence) may be tested as a unique intervention scenario for the cost-effective analysis.

### **9.6.3 Cost-effectiveness and cost-utility analysis**

First, we will calculate the incremental cost-effectiveness ratio (ICER) for the intervention overall compared to standard of care as:  $[(\text{CostIntervention} - \text{CostStandardofCare})] / [(\text{Infections AvertedIntervention} - \text{Infections AvertedStandardofCare})]$ . This value will give us the cost per HIV infection averted. We will use bootstrapping to calculate the confidence interval around this ratio. If we let  $\Delta X$  denote the total number of infections averted by the intervention relative to standard of care, the corresponding savings in averted HIV-related treatment costs equals  $T * \Delta X$ , where  $T$  is the (discounted at an annual rate of 3%) lifetime cost of medical care averted each time an incident HIV infection is averted. Thus, the net cost of the intervention can be calculated as  $C - T * \Delta X$ , where  $C$  is total costs. Similarly, the total number of QALYs saved by the intervention equals  $Q * \Delta X$ , where  $Q$  is the number (discounted at an annual rate of 3%) of QALYs saved by preventing a single HIV infection. Estimates of  $T$  and  $Q$  are available in the literature. We will use the most up-to-date values available for our analyses (current estimates of  $T$  are \$330,000 and  $Q$

are 5.83). The cost-utility ratio (the net cost per QALY saved) is thus  $(C - T^* \Delta X) / Q^* \Delta X$ . The intervention will be considered “cost-saving” if the net cost per QALY saved is negative. The intervention will be considered “cost-effective” if the cost-utility ratio is less than commonly-cited U.S. thresholds (e.g., \$100,000 per QALY saved). One-way sensitivity analyses will be performed for all input variables to determine which inputs the cost-effectiveness and cost-utility estimates are most sensitive to. We will explore implementation scenarios including the impact of generic drug pricing, one of the major determinants of PrEP cost-effectiveness.

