### 9.2 Power to detect effects in primary outcomes

A total of 396 participants will be enrolled at baseline to account for a 10% expected loss to followup during 12-months of study follow-up. With this sample size and assuming  $\alpha=0.05$  and two-sided significance, there will be 80% power to detect absolute differences between the intervention and control arms in the proportion of subjects with protective levels of TFV-DP of > 15.8% when the average proportion in the control group is 0.50. Power calculations were performed using PASS v.13 software (NCSS, LLC. Kaysville, Utah). Hypothesis is participants randomized to PrEP@Home will have higher levels of protection against HIV infection as

determined by levels of emtricitabine triphosphate (TFV-DP) than standard of care controls.

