### **9.4 Mathematical modeling**

Mathematical modeling will be used to estimate the potential impact of scaling-up PrEP@Home for MSM across the United States. This will be done by using a robust model that simulates HIV transmission across dynamic sexual partnership networks, which we have used to predict the impact and efficiency of CDC's PrEP guidelines for MSM. Model parameters related to PrEP persistence and adherence will be based on the efficacy results in Aims 1-2.1. Sensitivity analyses will vary levels of and heterogeneity in PrEP access, PrEP@Home uptake, and time-varying PrEP adherence. The aim of these models will be to address the question of how PrEP@Home could reduce HIV incidence in the population by improving persistence above levels currently observed in clinic-based PrEP demonstration projects. Modeling activities will also include extending our web-based PrEP forecasting tool for public health policymakers (<https://prism.shinyapps.io/cdcprep-guidelines>) to incorporate new parameter data and sensitivity analyses. Model outputs such as the cumulative number of infections averted (a measure of impact) and the number needed to treat to prevent one new infection (a measure of efficiency) will be fed into the cost-effectiveness analyses (Aim 3) as input parameters.

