### **9.6.1 Costing the intervention and standard of care arms**

Comprehensive cost analysis will be conducted to assess the cost of developing and implementing the PrEP@Home intervention. A micro-costing approach will be used along with the standard literature practice of itemizing the intervention components and attaching a dollar value to them. Two categories of costs will be defined: *developmental costs* (the initial or start-up

costs involving the time spent in developing the intervention) and *implementation costs* (on-going costs of delivering the intervention). The development costs will include costs from the first phase of the research including salaries and fringe benefits for intervention development staff, pilot testing of the intervention, study recruitment, screening, consenting, enrollment, and mailing systems; and piloting lab procedures. Implementation costs will include recruitment, salary and fringe benefits for an intervention coordinator, kit component, production and laboratory testing costs, drug costs (not paid by the study), and the as-needed cost of consultants and technical support, self-reported time participants spend adhering to the PrEP@Home intervention or standard of care, data management, and clinical costs. Participant's self-reported time spent involved in study activities will be translated into an opportunity cost, where participation incentives will be taken as a proxy of the cost of patient time and we will also use income data from study participants.

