Costing analysis for the standard of care arm within the cost-effectiveness analysis will be based on secondary literature estimating the health care and societal costs associated with PrEP for MSM in the US. To calculate personnel costs, we will multiply these hours by wage rates gathered from the Bureau of Labor Statistics and calculate an average cost per man receiving care in the standard of care arm. We will carefully track these ongoing costs during the 12 months of implementation (the time period of the analysis) using standardized data collection tools. Cost data will be collected by extraction from accounting records, budget records, external contracts, study case report forms, PrEP prescription receipt data; interviews with program implementers; and self-report from participants. Data will be entered into a standardized excel spreadsheet with embedded formulas to calculate the cost. These methods have been used by our research team for economic analyses for a variety of HIV prevention interventions including PrEP interventions. Costs will be discounted at an annual rate of 3%.

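### The bootstrap interval for cost per infection averted does not say what is resampled, and on either reading it leaves out literature-cost and model-parameter uncertainty; a probabilistic sensitivity analysis should replace it.

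*Combined protocol and SAP*

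**What the plan says.** Section 9.6.3 defines the ICER as incremental cost over incremental infections averted and adds "We will use bootstrapping to calculate the confidence interval around this ratio". It names no resampling unit and does not list the quantities resampled. No interval is described for the cost-utility ratio that follows.

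The inputs have different origins:
- **Infections averted (9.6.2):** "This will be estimated in our dynamic modeling activities". They are not counted in the trial.
- **Link from trial to model (9.4):** "Model parameters related to PrEP persistence and adherence will be based on the efficacy results in Aims 1-2.1". The same section then passes model outputs to Aim 3 as inputs.
- **Standard-of-care cost (9.6.1):** "Costing analysis for the standard of care arm within the cost-effectiveness analysis will be based on secondary literature". Some participant-level data cover both arms, including "self-reported time participants spend adhering to the PrEP@Home intervention or standard of care".

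Uncertainty is otherwise explored separately. Section 9.6.3 states "One-way sensitivity analyses will be performed for all input variables", and section 9.6.2 states "Each sensitivity analysis in the epidemic model (varying levels of access, coverage, and adherence) may be tested as a unique intervention scenario". No analysis that varies inputs jointly according to their uncertainty is described.

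Section 9.6.3 calls the intervention cost-saving if net cost per QALY saved is negative, and cost-effective if the ratio lies below a threshold such as $100,000.

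**The concern.** A bootstrap measures sampling error in the data that are resampled. Here the denominator is a simulation result and much of the comparator cost is a published figure. Neither varies when trial records are resampled, unless the model is re-run in each replicate and the literature inputs are given distributions. The plan says neither. One-way and scenario analyses show which inputs matter, but they do not widen the interval.

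At stake is a cost per infection averted reported with more precision than the evidence supports. There is also a decision rule that can give a favourable label to a programme that averts fewer infections at higher net cost.

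**Working it through.** **1. Reproduce the plan's design figure.** Section 9.2 gives 396 enrolled, 10% loss, control proportion 0.50, a difference of 15.8 points, and "two-sided significance, there will be 80% power to detect absolute differences". Section 5.2 gives 264 v 132. Evaluable numbers are 264 × 0.9 = 237.6 and 132 × 0.9 = 118.8. A pooled two-sided z-test at 0.05 gives power 0.819, or 0.787 with continuity correction. The detectable difference at 80% power is 15.4 or 16.0 points respectively. The stated 80% and 15.8 points lie between these values, so the design inputs can be used.

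**2. Sampling error of the trial effect at the design values.**
- SE = √(0.658 × 0.342/237.6 + 0.50 × 0.50/118.8) = √(0.000947 + 0.002104) = 0.0552.
- 95% CI = 0.158 ± 1.96 × 0.0552 = 0.050 to 0.266.
- Relative SE = 0.0552/0.158 = 0.35.

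If infections averted were proportional to this difference and incremental cost were fixed (both assumptions), the ICER would vary 0.266/0.050 ≈ 5-fold across the interval.

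**3. Reading A: each replicate re-estimates the effect and re-runs the model.** The trial effect is then carried through, but literature and other model inputs are not. Let CV_ext be their combined relative SE. The documents give no value, so a range is assumed. With independent errors on the relative scale, and participant-cost sampling error set aside:

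omitted share = CV_ext² / (CV_ext² + 0.35²); interval width relative to full width = √(1 − omitted share)

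| Assumed CV_ext | Variance omitted | Width relative to full |
|---|---|---|
| 0.1 | 8% | 96% |
| 0.2 | 25% | 87% |
| 0.3 | 42% | 76% |
| 0.5 | 67% | 57% |
| 1.0 | 89% | 33% |

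More than half of the variance is omitted only if CV_ext exceeds about 0.35.

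**4. Reading B: model output is held fixed and only costs are resampled.** The relative SE of 0.35 from step 2 is then also missing, on top of whatever is omitted in step 3.

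**5. Sign of the ratio.** Section 9.6.3 uses (C − TΔX)/(QΔX) with T = $330,000 and Q = 5.83. Take ΔX = −1 and, for illustration, C = 0. Net cost is +$330,000, QALYs saved are −5.83, and the ratio is 330,000/(−5.83) ≈ −$56,600. A positive C makes it more negative. The rule reads this as cost-saving, and it also lies below $100,000. Net monetary benefit gives the right sign: 100,000 × 5.83 × (−1) − 330,000 = −$913,000.

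**6. Can the denominator be negative?** At the design effect, a non-positive difference occurs in about 0.2% of simulated trials. At half that effect (7.9 points, an assumption), SE = √(0.579 × 0.421/237.6 + 0.25/118.8) = 0.056, z = 0.079/0.056 = 1.41, and the probability is about 8%. Section 10.2 itself allows that remote care might lower persistence or adherence.

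**The case against.** The strongest reply is that section 9.6.3 is brief rather than wrong. It does not say that participants alone are resampled, nor that model output is fixed. Since section 9.4 feeds trial results into the model, a well-built bootstrap could carry the trial's sampling error through to infections averted. That stands, and it is why the size of the shortfall cannot be stated. It does not rescue the literature costs or the other model parameters, which such a bootstrap would still leave out.

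A reader might go further and infer that the interval omits most of the uncertainty, is far too narrow, or reflects intervention-arm costs alone. The documents do not support this:
- Under reading A the omitted share runs from 8% to 89%, depending on an external CV that is not given.
- Section 9.6.1 collects participant-reported time under standard of care as well as under PrEP@Home.
- Setting the 5-fold range beside the precision of mean intervention cost would mislead. With an assumed SD/mean of 0.5 to 1.0 and n = 264, that half-width is 1.96 × (0.5 to 1.0)/√264 = 6% to 12%. The ICER numerator, however, is incremental cost. If standard-of-care cost were 80% of intervention cost (assumption), the same absolute error would be five times larger relative to the increment, 30% to 60%.
- The 5-fold figure is itself only illustrative. The model is a dynamic network model, and better persistence could also raise drug costs.

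It is also fair to say that scenario analyses are planned and that naming the resampling unit would close part of the gap. It would not bring literature and model uncertainty into the interval.

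**Conclusion.** The point holds as an under-specified and incomplete uncertainty analysis. On either reading the interval leaves out uncertainty in literature costs and in model parameters not taken from the trial. If model output is fixed, it also leaves out a trial effect with a relative SE of about 0.35 at the design values. The direction, understatement, follows from the plan's own description of its inputs. The amount does not, because the documents give no costs, infections averted or standard errors for the external inputs.

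The ratio problem is separate and needs no assumed variances: negative infections averted with positive net cost meet the stated cost-saving rule. How often this arises depends on the true effect. It is rare at the design effect and about 8% at half of it, if infections averted take the sign of the TFV-DP difference.

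This is a worthwhile, inexpensive improvement to Aim 3. The primary efficacy test is unaffected.

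**What to change.** Replace the bootstrap sentence in section 9.6.3 with a probabilistic sensitivity analysis:
1. In each draw, sample the intention-to-treat effect on the model's persistence and adherence parameters, other key model parameters, intervention cost (a bootstrap is suitable for this input), standard-of-care cost, T and Q. Run the epidemic model for that draw. Specify the distributions in advance.
2. Report incremental cost, and infections averted or QALYs, each with a 95% interval.
3. Report net monetary benefit, 100,000 × Q × ΔX − (C − T × ΔX), with a 95% interval. An acceptability curve is optional.
4. Keep the ICER as a point estimate, and keep the one-way analyses.
5. Apply the cost-saving label only when infections averted are positive.

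The cost is SAP wording, agreed input distributions, additional model runs and a wider interval. No new participant data are needed.

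### Section 9.6 does not put costs and infections averted on one time basis: ΔX has no stated horizon and is not discounted by year of infection

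*Combined protocol and SAP*

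**What the plan says.** *Costs.* Section 9.6.1 has costs tracked "during the 12 months of implementation (the time period of the analysis"), and then discounts costs at 3% a year. In the cost-utility formula of Section 9.6.3, C is simply total costs.

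*Effects.* Section 9.6.2 states: "The health effect is defined as the projected reduction in HIV incidence over time". It measures this by "the number of infections averted per unit person-time on the intervention" and by a number needed to treat. Section 9.4 describes a network model of national scale-up and passes its outputs to Aim 3, among them "the cumulative number of infections averted (a measure of impact").

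*Ratios.* Section 9.6.3 lets ΔX "denote the total number of infections averted by the intervention relative to standard of care". The cost-utility ratio is (C − T·ΔX)/(Q·ΔX), with T = $330,000 and Q = 5.83, each a per-infection value discounted at 3%. A negative ratio counts as cost-saving. A ratio below a threshold such as $100,000 per QALY counts as cost-effective. One-way sensitivity analyses cover all inputs, but neither horizon nor discount rate is named.

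Neither section gives a horizon for ΔX, discounts infections by when they occur, or explains how 12-month trial costs are matched to the modelled population.

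**The concern.** A cost-effectiveness ratio is interpretable only if its numerator and denominator cover the same people over the same period and are valued at the same date. Here the cost side is described as one year of a trial. The effect side is described as cumulative and projected from a population model.

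Discounting T and Q does not close the gap. Taken as present values at the time of infection, they discount what follows an infection. They do not bring an infection averted in year 10 back to program start, which is where costs are valued.

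The stake is the verdict under the plan's own decision rules. The choice of horizon and discounting can move a program across the $100,000 line or across zero. As the text stands, both could be settled after the results are known.

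**Working it through.** The plan gives no value for C, ΔX or either ratio, so there is no stated figure to reproduce. The check uses the plan's formula.

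**Inputs from Section 9.6:** T = $330,000; Q = 5.83; threshold $100,000 per QALY; discount rate 3%.

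**Assumptions:** effect horizon H from 1 to 20 years (not stated; the only multi-year modelling horizon in the documents is the ten years cited as background in Section 1); costs and infections averted spread evenly over H; T and Q are present values at the time of infection; C is incremental cost.

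**Step 1, break-even points.** Dividing through by ΔX gives

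(C − T·ΔX)/(Q·ΔX) = (C/ΔX − T)/Q.

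- Cost-saving limit: C/ΔX = $330,000 per infection averted.
- Threshold: C/ΔX = 330,000 + 100,000 × 5.83 = $913,000 per infection averted.

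**Step 2, the missing discount on ΔX.** With mid-year timing, the mean discount factor is f(H) = (1/H) Σ 1.03^−(t − 0.5), for t = 1 to H. An undiscounted ΔX overstates QALYs and treatment savings by 1/f − 1. The range in the table runs from start-of-year to end-of-year timing.

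| H (years) | f, mid-year | 1/f − 1, mid-year | Range |
|---|---|---|---|
| 1 | 0.9853 | 1.5% | 0–3% |
| 5 | 0.9296 | 7.6% | 6–9% |
| 10 | 0.8657 | 15.5% | 14–17% |
| 20 | 0.7549 | 32% | 31–34% |

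**Step 3, effect on cost per QALY.** Take a program whose consistent value is $913,000 per infection averted, which is exactly $100,000 per QALY.

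(a) Costs over H years, discounted, against H years of undiscounted infections: apparent C/ΔX = 913,000 × f.

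(b) Costs of 12 months against H years of undiscounted infections: apparent C/ΔX = 913,000 × 0.9853/H.

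| H (years) | (a) C/ΔX | (a) per QALY | (b) C/ΔX | (b) per QALY |
|---|---|---|---|---|
| 1 | $899,606 | $97,703 | $899,606 | $97,703 |
| 5 | $848,706 | $88,972 | $179,921 | −$25,743 |
| 10 | $790,403 | $78,971 | $89,961 | −$41,173 |
| 20 | $689,269 | $61,624 | $44,980 | −$48,888 |

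Example, (a) at 10 years: (790,403 − 330,000)/5.83 = $78,971. Under (b), cost per infection averted is understated about H-fold: 913,000/89,961 ≈ 10 at 10 years. From 5 years on, this program would be labelled cost-saving.

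**Step 4, direction.** ΔX enters the ratio only through C/ΔX. Omitting its discount multiplies C/ΔX by f < 1. If C and ΔX are positive, the ratio falls and looks better. If C is negative, C/ΔX moves up towards zero and the ratio looks less favourable.

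**The case against.** The strongest reply is that no mismatch is shown. Section 9.6.1 calls the 12 months the period of the analysis, and Section 9.6.2 expresses the effect per unit of person-time, so ΔX could be confined to the same 12 months. In that case the numbers match and the missing discount is worth at most 3%. The parts of a matched calculation are also planned: a cost per participant (Section 9.6), an average cost per man in standard of care (Section 9.6.1) and infections averted per person-time (Section 9.6.2). A rate and a total are not contradictory, since a total is a rate times person-time.

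Much of this stands, and it rules out several stronger readings:

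- A reader might infer that the plan will divide one year of trial cost by many years of a population's infections. No section says so. That pairs the shortest reading of C with the longest reading of ΔX.
- A reader might infer that discounting T and Q itself conflicts with an undiscounted ΔX. It does not. Only the step from infection back to program start is missing.
- A reader might infer that the bias always flatters the intervention. Section 1 says home care could save money, and then the bias reverses. Also, if C is read literally as total rather than incremental cost, the cost-utility ratio is pushed the other way.

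The reply does not settle the matter. Annual discounting of costs has little purpose over 12 months, and a cumulative projection over time fits a one-year effect poorly. If the horizon is longer, the tracked costs do not cover it. The plan never says how unit costs and modelled person-time are joined. Varying inputs one at a time cannot repair two sides on different bases.

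**Conclusion.** The point holds conditionally. Sections 9.4 and 9.6 do not put costs and infections averted on one horizon, population and discounting basis, and the formulas as written give a wrong ratio for any effect horizon beyond one year. That the planned horizon does exceed one year is not established.

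Where it does, and ΔX and incremental cost are both positive, both ratios are too favourable. From the discounting omission alone, a program at the threshold would appear about $21,000 per QALY better at 10 years (100,000 − 78,971) and about $38,400 better at 20 years (100,000 − 61,624). A full mismatch of periods could produce a false cost-saving verdict. These sizes rest on assumed horizons, even timing, and T and Q valued at infection.

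The point concerns Aim 3 only and does not touch the primary outcome. It should be corrected before the economic analysis is run.

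**What to change.** In Section 9.6.3:

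1. State one horizon and one population for both costs and infections averted.
2. Use the 12-month trial costs only as unit costs: intervention minus standard of care per person-year, applied to modelled person-time in the same model run that yields the infections. A per-person-year cost is needed in any case, because participants enrolled after May 2022 are followed for only 6 months (Sections 3.1 and 6.3).
3. Discount costs and each infection averted at 3% from program start, so that ΔX is a discounted sum, and define C as incremental cost.
4. Add horizon and discount rate to the one-way sensitivity analyses.

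The cost is revised wording and one extra model output, with no new data collection. The ratios may become less favourable.

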## **9.6 Cost-effectiveness and cost-utility analyses**

We will conduct an economic analysis from both the payer perspective (the cost to the party implementing the program) and societal perspective (the payer costs plus the cost to the participant for participating in the program) to estimate the cost, cost-effectiveness, and cost-utility of the intervention relative to standard of care. Including the societal perspective accounts for costs to all parties, acknowledges the value of competing uses for societies' resources, and maximizes comparability with other cost-effectiveness analyses. The cost analysis will calculate the overall cost of implementing the program, the cost per participant, and the cost per person contacted.

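### The cost-utility ratio in 9.6.3 sets total cost against incremental infections averted, and its cost-saving rule does not require that any infections be averted

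*Combined protocol and SAP*

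**What the plan says.** Section 9.6 sets out to estimate the cost, cost-effectiveness and "cost-utility of the intervention relative to standard of care". Section 9.6.3 then defines two ratios.

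- The ICER divides intervention cost minus standard-of-care cost by the corresponding difference in infections averted. Numerator and denominator are both incremental.
- For the cost-utility ratio, ΔX is introduced to "denote the total number of infections averted by the intervention relative to standard of care". The section says "the net cost of the intervention can be calculated as" C − T·ΔX, with C described only as total costs. QALYs saved are Q·ΔX, so the ratio is (C − T·ΔX)/(Q·ΔX). The stated values are T = 330,000 dollars and Q = 5.83.

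Two labels are read from the second ratio. The intervention is cost-saving "if the net cost per QALY saved is negative", and cost-effective if the ratio lies below a threshold such as 100,000 dollars per QALY. Neither rule has a condition on the sign of ΔX, and nothing else in 9.6 supplies one.

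Section 9.6.1 counts drug costs and laboratory testing among implementation costs. It separately plans to "calculate an average cost per man receiving care in the standard of care arm". That figure does not appear in the cost-utility formula.

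**The concern.** **Comparator.** Participants in both arms are prescribed PrEP and need monitoring, so both arms incur drug and care costs. If C is the intervention's total cost, those costs are charged in full against an effect that is only the difference between arms. A beneficial program then looks dearer than it is against its comparator. The planned scenario on "the impact of generic drug pricing, one of the major determinants of PrEP cost-effectiveness" would also move the ratio through the whole drug cost rather than through the between-arm difference.

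**Sign.** A negative ratio can mean lower net cost with QALYs gained, or higher net cost with QALYs lost. The rule treats the two alike.

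The Aim 3 labels are read from this ratio. The two faults pull in opposite directions, so neither can be excused as conservative. Negative ΔX is within the plan's scope. Section 10.2 accepts that remote care could leave some participants with poorer persistence or adherence. Section 9.6.2 says each sensitivity scenario on access, coverage and adherence "may be tested as a unique intervention scenario for the cost-effective analysis".

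**Working it through.** The plan states no value for C, for standard-of-care cost or for ΔX, and no cost-utility result, so there is no figure of its own to reproduce.

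**Inputs.** T = 330,000, Q = 5.83 and the 100,000 threshold come from 9.6.3. All costs and all ΔX values below are assumptions. Amounts are in US dollars.

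**Step 1: algebra for ΔX > 0.** Replacing total cost by the cost difference lowers the ratio by exactly CostSoC/(Q·ΔX). The label limits on whichever cost is used are:

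- cost-saving: cost < 330,000·ΔX
- cost-effective: cost < (330,000 + 100,000 × 5.83)·ΔX = 913,000·ΔX

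**Step 2: size of the comparator fault, per 100 person-years.** Case A assumes 10,000 total and 1,000 incremental per person-year. Case B assumes 5,000 and 500.

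| ΔX | A, as written | A, incremental | B, as written | B, incremental |
|---|---|---|---|---|
| 0.25 | 629,503 | 12,007 | 286,449 | −22,298 |
| 0.5 | 286,449 | −22,298 | 114,923 | −39,451 |
| 1.0 | 114,923 | −39,451 | 29,160 | −48,027 |
| 2.0 | 29,160 | −48,027 | −13,722 | −52,316 |

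Example, case A at ΔX = 0.5: (1,000,000 − 165,000)/2.915 = 286,449, against (100,000 − 165,000)/2.915 = −22,298. The gap is 900,000/2.915 = 308,748.

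Ranges of ΔX over which the label changes:

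- Case A, cost-effective: 100,000/913,000 = 0.11 to 1,000,000/913,000 = 1.10. Cost-saving: 100,000/330,000 = 0.30 to 1,000,000/330,000 = 3.03.
- Case B, cost-effective: 0.055 to 0.55. Cost-saving: 0.15 to 1.52.

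For positive ΔX outside these ranges, the two formulas give the same label.

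**Step 3: other standard-of-care shares.** Both cases put 90% of the cost in standard of care. Now take an intervention cost of 2.0 million and ΔX = 2, so Q·ΔX = 11.66. As written, the ratio is (2,000,000 − 660,000)/11.66 = 114,923.

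| Standard-of-care cost | Share | Incremental ratio | Overstatement |
|---|---|---|---|
| 1.0 million | 50% | 29,160 | 85,763 |
| 1.5 million | 75% | −13,722 | 128,645 |
| 1.9 million | 95% | −48,027 | 162,950 |

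All three rows pass the threshold incrementally and fail it as written. A smaller share narrows the problem. At 50% and ΔX = 3 the ratios are 57,747 and 572, and the label is the same.

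**Step 4: sign.** If C ≥ 0 and ΔX < 0, the numerator is positive and the denominator negative. The ratio is then always negative, whatever the costs. At ΔX = −0.5 per 100 person-years:

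- C as total, 500,000: (500,000 + 165,000)/(−2.915) = −228,130, labelled cost-saving.
- C as incremental, +50,000: 215,000/(−2.915) = −73,756, also labelled cost-saving. Net monetary benefit is 583,000 × (−0.5) − 215,000 = −506,500.
- C as incremental, −300,000 (cheaper but less effective): (−300,000 + 165,000)/(−2.915) = 46,312, which passes the threshold. Net monetary benefit is −291,500 + 135,000 = −156,500.

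The ratio cannot separate opposite results. An incremental cost of +0.5 million with ΔX = −2 and one of −0.5 million with ΔX = +2 both give −99,485.

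**Step 5: the threshold rule when ΔX < 0.** Multiplying through by a negative Q·ΔX reverses the inequality, so a ratio below 100,000 is equivalent to C > 913,000·ΔX. With C incremental, net monetary benefit is 913,000·ΔX − C, which is negative under exactly that condition. For ΔX < 0 the rule therefore passes precisely the results it should reject.

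**The case against.** The strongest reply is that C was meant to be incremental. In the same paragraph the word total also qualifies quantities that are plainly relative to standard of care, the ICER writes out the cost difference, and 9.6 frames the whole analysis against standard of care. That reading is possible. What stands is that the first fault is a mismatch in the text, not proof of what would be computed. The text still allows either calculation, and the sign fault survives under both.

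Second, the magnitudes are illustrative. The costs and ΔX values are assumed, and the overstatement depends on the standard-of-care share. This stands. The tables show when the label changes, not that it will change in this trial.

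Third, drug cost need not be equal between arms. If the intervention improves persistence, its participants use more drug, and price properly enters the incremental cost. This also stands: a generic-price scenario is sound under either definition. The objection to it is limited to the part of drug cost that both arms share.

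Fourth, the section speaks of reductions and of QALYs saved, which suggests benefit was presupposed, and analysts would see a negative ΔX before applying a label. That is a reason to write the condition down. The DSMB wording in 8.1 about the intervention performing worse concerns stopping the trial and is weak support for a negative modelled ΔX. Sections 9.6.2 and 10.2 are the better basis.

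**Conclusion.** The concern holds. As written, the ratio compares total cost with an incremental effect, which for ΔX > 0 overstates cost per QALY by CostSoC/(Q·ΔX). Under the assumed costs in case A this changes at least one label for ΔX from 0.11 to 3.03 per 100 person-years. This half depends on taking C literally.

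The sign fault does not depend on the reading of C or on any assumed cost. Every ΔX < 0 with C ≥ 0 is called cost-saving, and with incremental C the threshold rule is exactly reversed. It takes effect only if a base case or scenario produces ΔX < 0.

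This should be corrected before the Aim 3 analysis. It does not touch the primary outcome or the ICER point-estimate formula.

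**What to change.** In 9.6.3:

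1. Define C as intervention cost minus standard-of-care cost, the same difference the ICER uses.
2. Report net incremental cost (C − T·ΔX) and incremental QALYs (Q·ΔX) separately, alongside the ratio.
3. Call the intervention cost-saving only if ΔX > 0 and C − T·ΔX < 0.
4. Compare the ratio with the threshold only if ΔX > 0. Otherwise decide by dominance or, as one acceptable option, by incremental net monetary benefit, 100,000·Q·ΔX − (C − T·ΔX). At ΔX = 0 the ratio is undefined and only costs can be compared.

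Step 1 alone is not enough, as the incremental examples at ΔX = −0.5 show. The change is a few lines of text. It needs no new data, because 9.6.1 already plans an average standard-of-care cost.
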